2.1. Primary Endpoint

Describe the proportion of patients discontinued from study treatment due to adverse events through the last treatment visit.

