7.4. Week 4 (\pm 3 Days)

- Complete the following assessments: IGA, BSA and EASI
- Review and record AEs and update concomitant medication and procedure/therapy information
- Measure vital signs
- Draw a pre-dose blood sample for PK and ADA testing
- Conduct urine pregnancy test (WOCBP only)
- Administer study drug
- Confirm moisturizer use

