7.6. Patient Disposition

The following patient disposition summaries will be provided (details of the analysis populations can be found in Section [7.1.1](#)):

- The total number and percentage of patients entering each statistical analysis population is defined in Section [7.1.1](#) (analysis population: all entered patients).
- The number and percentage of patients who entered the study, were treated, and screen failed will be provided overall and by screen fail reason (analysis population: all entered patients).
- The number and percentage of patients who were treated and completed treatment, and the number and percentage of patients who discontinued the treatment at any time, by primary reason for discontinuation of treatment (analysis population: safety population).

- The primary endpoint of Study KGAE is the proportion of patients discontinued from study treatment due to AEs through the last treatment visit.
- The number and percentage of patients who were treated and completed the study, and the number and percentage of patients who discontinued the study at any time, by primary reason for discontinuation (analysis population: safety population).

All patients who were treated (i.e., in the safety population) and discontinued from study treatment will be listed together with the discontinuation reason, and the timing of discontinuation from the study will be reported.

Patient allocation by region, country, and center/site will be summarized with the number of patients who entered the study, number of treated patients, number of patients discontinued from study treatment, and number of patients discontinued from the study.

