7.10. Efficacy Analyses

[Table KGAE.7.3](#) includes the description and derivation of the efficacy measures and endpoints.

For categorical parameters, the number and percentage of patients in each category will be presented, as well as a 95% confidence interval for the percentage. The 95% confidence interval

will be constructed using the asymptotic method, without continuity correction (that is, the normal approximation to the binomial distribution). For continuous parameters, descriptive statistics will include n (number of patients), mean, standard deviation, median, minimum, and maximum. These summaries will be provided for the data as-observed, and after implementation of LOCF and MCMC-MI imputation methods.

The IGA, EASI, and BSA will be reported by clinic visit.

Table KGAE.7.3. Description and Derivation of Efficacy/Health Outcomes Measures and Endpoints

Measure	Description	Variable	Derivation/Comment	Imputation Approach if Missing Components
Investigator’s Global Assessment (IGA)	The IGA is a static assessment and rates the severity of a patient’s AD. The IGA is comprised of a 5-point scale ranging from 0 (clear) to 4 (severe), and a score is selected using descriptors that best describe the overall appearance of the lesions at a given time point.	IGA score	Single item. Range: 0-4 0 represents “clear” 4 represents “severe”	Single item, missing if missing
		
 IGA (0,1) with ≥2-point improvement^a IGA (0) 	
 Observed score of 0 or 1 and change from baseline ≤-2 Observed score of 0 	Missing if baseline or observed value is missing Single item, missing if missing

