Body Surface Area (BSA) Affected by AD	The BSA assessment estimates the extent of disease or skin involvement with respect to AD and is expressed as a percentage of total body surface. BSA will be determined by the investigator or designee using the patient palm = 1% rule.	BSA score	$BSA_{Total} = BSA_{head\ and\ neck} + BSA_{trunk} + BSA_{upper\ limbs} + BSA_{lower\ limbs}$	NA: partial assessments cannot be saved.
		Change from baseline in BSA score ^a	Change from baseline: observed BSA score - baseline BSA score	Missing if baseline or observed value is missing.
Dermatology Life Quality Index (DLQI)	The DLQI is a validated, dermatology-specific, patient-reported measure that evaluates a patient’s HRQoL. This questionnaire has 10 items that are grouped in 6 domains, including symptoms and feelings, daily activities, leisure, work and school, personal relationships, and treatment. The recall period of this scale is over the “last week”. Response categories and corresponding scores are: Very much = 3 A lot = 2 A little = 1 Not at all = 0	DLQI total score	A DLQI total score is calculated by summing all 10 question responses and has a range of 0-30 (less to more impairment) (Finlay and Khan 1994; Basra et al. 2008).	Score of 1 unanswered question = 0; If 2 or more questions are missing, the total score is missing. Note: #7B could be a valid missing while #7A is not “No.” That is, #7 should be considered as 1 question.
		DLQI (0,1) in patients who had baseline DLQI score >1	A DLQI (0,1) response is defined as a postbaseline DLQI total score of 0 or 1. A DLQI total score of 0-1 is considered as having no effect on a patient’s HRQoL (Khilji et al. 2002; Hongbo et al. 2005).	Missing if DLQI total score is missing
		4-point improvement in patients who had baseline DLQI score $\geq 4^a$	Change from baseline ≤ -4	Missing if baseline is missing or observed value is missing.

Not relevant = 0
 
Scores range from 0-30, with higher scores indicating greater impairment of QoL. A DLQI total score of 0-1 is considered as having no effect on a patient’s HRQoL (Hongbo et al. 2005), and a 4-point change from baseline is considered as the minimal clinically important difference threshold (Khilji et al. 2002; Basra et al. 2015).
	
DLQI total score change from baseline^a
	
Calculated as: observed DLQI (total score) - baseline DLQI (total score)
	
Missing if baseline or observed value is missing

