Children’s Dermatology Life Quality Index (CDLQI)	The CDLQI is designed to measure the impact of any skin disease on the lives of children. Patients ≤16 years will complete the CDLQI and should continue to complete the CDLQI for the duration of the study. The scoring of each question is: 
 • Very much = 3 • Quite a lot = 2 • Only a little = 1 • Not at all = 0 • Question unanswered = 0 • Question 7: 'Prevented school' (text-only questionnaire) = 3 	CDLQI total score	A CDLQI total score is calculated by summing all 10 question responses and has a range of 0-30 (less to more impairment) (Waters A et al. 2010).	Score of 1 unanswered question = 0; If 2 or more questions are missing, the total score is missing.
		CDLQI (0,1) in patients who had baseline CDLQI score >1	A CDLQI (0,1) response is defined as a postbaseline CDLQI total score of 0 or 1.	Missing if CLQI total score is missing
		CDLQI total score change from baseline ^a	Calculated as: observed CDLQI (total score) - baseline CDLQI (total score)	Missing if baseline or observed value is missing
		CDLQI symptoms and feelings domain	Sum of responses of questions 1 and 2: 1. Over the last week, how itchy, “scratchy”, sore or painful has your skin been? 2. Over the last week, how embarrassed or self conscious, upset or sad have you been because of your skin?	If 1 question in a domain is missing, that domain is missing.
		CDLQI sleep domain	Response of question 9 9. Over the last week, how much has	Single item, missing if missing

			your sleep been affected by your skin problem?	
		CDLQI leisure domain	
Sum of responses of questions 4, 5, and 6:
 
4. Over the last week, how much have you changed or worn different or special clothes/shoes because of your skin?
 
5. Over the last week, how much has your skin trouble affected going out, playing, or doing hobbies?
 
6. Over the last week, how much have you avoided swimming or other sports because of your skin trouble?
	If 1 question in a domain is missing, that domain is missing.
		CDLQI school or holiday domain	
Responses of questions 7:
 
If select 'Prevented school', score = 3
 
Last week,  If school time: was it school time? Over the last week, how much did your skin affect your school work?
 
OR
 
was it  If holiday time: holiday time? How much over the last week, has your skin problem interfered with your enjoyment of the holiday?
	Single item, missing if missing

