7.11. Health Outcomes/Quality-of-Life Analyses

The description and derivation of the DLQI/CDLQI and the PROMIS® anxiety and depression are described in [Table KGAE.7.3](#). For categorical parameters, the number and percentage of patients in each category will be presented, as well as a 95% confidence interval for the percentage. The 95% confidence interval will be constructed using the same method described for the efficacy endpoints. For continuous parameters, descriptive statistics will include n (number of patients), mean, standard deviation, median, minimum, and maximum. These summaries will be provided for the data as-observed, and after implementation of LOCF and MCMC-MI imputation methods. Patient-Reported Outcomes Information System and DLQI/CDLQI will be reported by clinic visit.

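### SAP 7.10 and 7.11 give every response percentage an uncorrected Wald 95% interval, which breaks down near 0% and 100%, and the readable text has no fallback

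*SAP*

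**What the plan says.** SAP 7.10 presents every categorical efficacy parameter as a count, a percentage and a 95% confidence interval. The interval "will be constructed using the asymptotic method, without continuity correction (that is, the normal approximation to the binomial distribution". SAP 7.11 extends this to the health outcomes: "The 95% confidence interval will be constructed using the same method described for the efficacy endpoints". Both sections apply the summaries to as-observed, LOCF and MCMC-MI data.

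Three further provisions determine which cells the rule meets:

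- **By-visit reporting.** "The IGA, EASI, and BSA will be reported by clinic visit" (SAP 7.10). The first post-baseline assessment is at Week 4, where Protocol 7.4 says: "Complete the following assessments: IGA, BSA and EASI".
- **Strict response variables.** SAP Table KGAE.7.3 includes IGA (0) and EASI-90.
- **A split questionnaire.** "Patients ≤16 years will complete the CDLQI and should continue to complete the CDLQI for the duration of the study" (SAP Table KGAE.7.3). The DLQI variables therefore rest on patients older than 16. They are restricted further by baseline score: above 1 for DLQI (0,1), and at least 4 for the variable described as "4-point improvement in patients who had baseline DLQI score" of that size.

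The readable text has no rule for 0%, 100%, sparse counts or limits outside 0–100%. SAP 7.3.2 and 7.3.3 (LOCF and MCMC-MI) and the sample-size sections (Protocol 9.9, SAP 6.2) are blacked out, and nothing here relies on them.

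**The concern.** The Wald interval takes its width from the observed proportion alone. As that proportion approaches 0 or 1 the estimated standard error shrinks to zero, so the interval becomes too short, is centred too close to the boundary, and can cross it. Three things follow: zero-width intervals that imply certainty, impossible limits, and coverage below the stated 95%.

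Two kinds of cell are exposed. The first is a by-visit percentage near an extreme. Protocol 4.1 requires a baseline IGA of 3 or more, so IGA (0) at Week 4 needs a fall of at least 3 points in four weeks. The second is the DLQI responder set, where the denominator may be small.

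The study has one arm and no inferential testing, and these are the only confidence intervals in the readable SAP. They are what a reader will use to judge the precision of the response rates.

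**Working it through.** **Starting point.** The plan states no interval width, coverage or precision target, so there is no figure of its own to reproduce.

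**Inputs**

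- 95% level, z = 1.96, z² = 3.8415 (SAP 7.10).
- Full sample n = 200, the approximate planned size (SAP 6.1).
- DLQI denominator: not documented. If the 200 patients are spread evenly over the six one-year ages 12 to 17, then 200/6 ≈ 33 are aged 17 and 2 × 200/6 ≈ 67 are past their 16th birthday. I also use n = 20 to allow for the baseline-score cut and dropout.
- True response rates: not documented, so ranges are shown.

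**Step 1: when the interval fails.** Let k be the number of responders (or, by symmetry, of non-responders), with p = k/n. The limits are p ± z√(p(1−p)/n).

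- At k = 0 the standard error is zero, so the width is zero.
- For k > 0, the limit crosses the boundary when p² < z²p(1−p)/n, that is, when k < n·z²/(n + z²).

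| n | cut-off for k |
|---|---|
| 13 | 2.97 |
| 14 | 3.01 |
| 33 | 3.44 |
| 67 | 3.63 |
| 200 | 3.77 |

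The cut-off rises with n but never reaches z² = 3.84. So k = 1, 2 and 3 fail at every n of 14 or more, and k = 4 does not. At n = 200, k = 4 gives 0.06% to 3.94%.

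**Step 2: example limits**

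| Result | Wald | Wilson |
|---|---|---|
| 0/200 | 0% to 0% | 0% to 1.88% |
| 2/200 | −0.38% to 2.38% | 0.27% to 3.57% |
| 120/200 | 53.2% to 66.8% | 53.1% to 66.5% |
| 20/33 | 43.9% to 77.3% | 43.7% to 75.3% |
| 31/33 | 85.8% to 102.1% | 80.4% to 98.3% |
| 65/67 | upper limit 101.1% | upper limit 99.2% |

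As one worked case, 31/33 = 0.9394. The standard error is √(0.9394 × 0.0606/33) = 0.0415, and 1.96 × 0.0415 = 0.0814, giving 0.858 to 1.021. For 33/33, Wald gives 100% to 100%, while the exact lower limit is 0.025^(1/33) = 89.4%.

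**Step 3: coverage.** For each true rate, sum the Binomial(n, rate) probabilities over all k whose interval contains that rate. Then average over an even grid of 801 rates in each range.

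| n | True rate | Wald | Wilson |
|---|---|---|---|
| 20 | 30–70% | 92.4% | 95.1% |
| 20 | 70–90% | 90.4% | 95.5% |
| 20 | 85–98% | 76.3% | 95.8% |
| 33 | 30–70% | 93.5% | 95.1% |
| 33 | 70–90% | 91.8% | 95.2% |
| 33 | 85–98% | 84.1% | 95.7% |
| 67 | 30–70% | 94.3% | 95.0% |
| 67 | 70–90% | 93.4% | 95.1% |
| 67 | 85–98% | 90.4% | 95.4% |
| 200 | 20–80% | 94.7% | 95.0% |

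At n = 200 and a single true rate of 1%, Wald covers 86.5% and Wilson 94.8%.

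**Step 4: how likely is failure in the full sample?** The binomial probability of 0 to 3 responders out of 200 is 85.8% at a true rate of 1%, 43.1% at 2% and 0.9% at 5%.

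**The case against.** The strongest defence is that little depends on these intervals. SAP 7.1.2 rules out inferential testing, SAP 7.16 rules out early stopping for efficacy, and the primary endpoint has no interval in the readable text, so the method does not touch it. Counts and percentages appear beside each interval, so an absurd limit would be visible. At n = 200, average coverage over true rates of 5–95% is 94.5% for Wald and 95.0% for Wilson. The lowest average, 76.3%, needs two undocumented assumptions together: 20 DLQI patients and a true rate of 85–98%. IGA (0) and DLQI (0,1) are not marked as secondary endpoints in Table KGAE.7.3. The method is also a named, prespecified choice: the Version 3 revision table records added detail on interval construction.

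Most of this stands as a limit on importance. It does not rescue the rule. EASI-90 and the DLQI 4-point improvement are marked secondary. A visibly wrong limit is still wrong, and under-coverage is not visible at all. A prespecified method should work for whatever counts occur, particularly when a replacement costs almost nothing in the middle of the range.

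The blacked-out SAP 7.3.3 is a real limit. It may already define a pooled interval, and the count rule in Step 1 does not carry over directly to pooled percentages. The absence of a fallback can be asserted only for the readable text.

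**Conclusion.** The point holds. The stated rule gives zero-width or out-of-range intervals whenever a percentage based on 14 or more patients lies within 3 patients of 0% or 100%, and it under-covers near those extremes. That much is arithmetic and needs no assumption about this trial.

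How often it will happen here cannot be known, because response rates and DLQI numbers are undocumented. In the full sample, out-of-range or zero-width results are likely only at true rates of about 2% or less (or 98% or more). In an assumed DLQI set of 20 to 67 patients, average coverage is 90.4–93.4% at true rates of 70–90% and 76.3–90.4% at 85–98%. Full-sample IGA (0,1) and EASI-75 rates between 20% and 80% would barely change, and DLQI rates between 30% and 70% only slightly. The sponsor should correct the rule, but no conclusion of the study depends on it.

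**What to change.** In SAP 7.10, replace the asymptotic method with the Wilson (score) 95% interval for as-observed and LOCF percentages, or with Clopper-Pearson if guaranteed coverage is preferred. SAP 7.11 then inherits the change. For MCMC-MI percentages, use a score- or logit-based pooled interval so that tables shown side by side use one family, unless SAP 7.3.3 already specifies one.

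The cost is a short SAP edit, a SAS option for the as-observed and LOCF tables, and a little programming for the pooled interval. Some intervals become asymmetric or slightly wider. Clopper-Pearson is conservative: at n = 33 its average coverage is 96.7% over true rates of 30–70% and 98.2% over 85–98%.

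One optional addition, which is not an error in the plan: the primary objective is worded "Describe the proportion of patients discontinued from study treatment due to adverse events through the last treatment visit", and SAP 7.6 plans only a number and percentage for it. A Clopper-Pearson 95% interval there would show its precision: 0–1.83% for 0/200, 0.55–5.04% for 4/200 and 2.42–9.00% for 10/200. SAP 7.13.2 refers to compound-level safety standards that could not be checked. If they already specify an interval, cite that instead.

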7.11. Health Outcomes/Quality-of-Life Analyses

The description and derivation of the DLQI/CDLQI and the PROMIS® anxiety and depression are described in [Table KGAE.7.3](#). For categorical parameters, the number and percentage of patients in each category will be presented, as well as a 95% confidence interval for the percentage. The 95% confidence interval will be constructed using the same method described for the efficacy endpoints. For continuous parameters, descriptive statistics will include n (number of patients), mean, standard deviation, median, minimum, and maximum. These summaries will be provided for the data as-observed, and after implementation of LOCF and MCMC-MI imputation methods. Patient-Reported Outcomes Information System and DLQI/CDLQI will be reported by clinic visit.

7.12. Bioanalytical and Pharmacokinetic/Pharmacodynamic Methods

Details of PK/PD analyses can be found in a separate PK/PD analysis plan. Pharmacokinetics is one of the study's secondary endpoints.

7.13. Safety Analyses

The planned analyses of safety data will be performed with an intent to maintain consistency with compound-level standard safety analyses. These standards are based on internal standards which were informed by CDISC standards, regulatory guidance (e.g., FDA Clinical Review Template), and cross-industry standardization efforts (e.g., PhUSE white papers from the Standard Analyses and Code Sharing Working Group provided in the PhUSE Computational Science Deliverables Catalog [WWW]).

The laboratory (including hormone), vital sign (including growth), and immunogenicity safety summaries will be based on the safety population. The extent of exposure and AE tables will be based on the safety population.

These analysis populations are fully defined in [Table KGAE.7.1](#).

Not all displays described in this section will necessarily be included in the CSRs. Any display described and not provided in the CSR would be available upon request. Not all displays will necessarily be created as a "static" display. Some may be incorporated into interactive display tools instead of or in addition to a static display. Any display created interactively will be included in the CSR if deemed relevant to the discussion.

7.13.1. Extent of Exposure

A by-patient listing of exposure duration with the number of active injections and total dose will be provided.

The duration of exposure will be calculated as:

$$\begin{aligned} \text{Duration of exposure (days)} \\ &= \text{Date of last visit (scheduled or unscheduled) in the Treatment Period} \\ &\quad - \text{Date of first dose} + 1 \end{aligned}$$

Drug interruption time period due to the use of systemic rescue therapies will not be removed from study drug exposure calculations.

The number and percentage of patients in each of the following categories will be included in the summaries:

- >0, ≥7 days, ≥14 days, ≥30 days, ≥60 days, ≥90 days, ≥112 days, ≥120 days, ≥150 days, ≥183 days, ≥210 days, and ≥273 days, ≥365 days; note that patients may be included in more than 1 category.
- >0 to <7 days, ≥7 to <14 days, ≥14 to <30 days, ≥30 to <60 days, ≥60 to <90 days, ≥90 to <120 days, ≥120 to <150 days, ≥150 to <183 days, ≥183 to <210 days, ≥210 to <273 days, ≥273 to <365 days, and ≥365 days)

Additional exposure ranges may be considered if necessary.

The summaries will also include the following information:

- total exposure in patient years, calculated as:

$$\begin{aligned} & \textit{Total exposure in patient years} \\ &= \frac{\textit{Sum of duration of exposures for all patients in treatment group}}{365.25} \end{aligned}$$

- mean and median total dose; total dose (in mg) is calculated by the number of active injections taken multiplied by 250.
- Total number of injections received will be derived from the *Study Drug Administration* eCRF and use the response to the question, “Please select the number of syringes successfully injected,” in the Dosing Diary.

7.13.2. Adverse Events

A TEAE is defined as an event that first occurred or worsened in severity after baseline (i.e., AEs with an onset date on or after the date of the first injection of study drug). The MedDRA lowest-level term will be used in the treatment-emergent computation. The maximum severity for each lowest-level term during the baseline period will be used as baseline. The treatment period will be included as postbaseline for the summaries. For events with a missing severity during the baseline period, the events will be treated as ‘mild’ in severity for determining treatment-emergence. Events with a missing severity during the postbaseline period will be treated as ‘severe’, and treatment-emergence will be determined by comparing to baseline severity. For events occurring on the day of first taking study medication, the events will be assumed to be posttreatment.

The planned summaries for AEs are provided in [Table KGAE.7.4](#) and are described more fully in compound-level safety standards and in the AE-related PhUSE white paper [Analysis and Displays Associated with Adverse Events: Focus on Adverse Events in Phase 2-4 Clinical Trials and Integrated Summary Document (PhUSE 2017)].

Summary tables, as described in [Table KGAE.7.4](#), will be presented for the safety population. Summary tables will include the number and percentage of patients reporting an event. For events that are gender-specific (as defined by MedDRA), the number of participants at risk will include only patients from the given gender.

Table KGAE.7.4. Summary Tables/Listings Related to Adverse Events

Summaries	Population (Section 7.1.1)
Overview of AEs	Safety
Summary of TEAEs by PTs	Safety
Summary of TEAEs by PTs within SOC	Safety
Summary of TEAE PTs by maximum severity	Safety
Summary of SAEs by PT within SOC	Safety
Summary of AEs leading to treatment discontinuation by PT with SOC	Safety
Summary of TEAEs possibly related to study drug by PTs within SOC	Safety
Listing of SAEs (including Death)	Safety
Listing of primary AEs leading to study treatment discontinuation	Safety
Listing of TEAEs (for Japan submission only)	Safety

Abbreviations: AE = adverse event; PT = Preferred Term; SAE = serious adverse event; SOC = System Organ Class; TEAE = treatment-emergent adverse event.

